15. SAFETY MEASUREMENTS

15.1 Definitions

An Adverse Event (AE) in this trial is any untoward medical occurrence in a participant to whom a trial intervention or procedure has been delivered, including occurrences which are not necessarily caused by or related to that intervention or procedure.

An AE can therefore be any unfavourable and unintended sign (including abnormal laboratory results), symptom or disease temporally associated with the use of the trial

intervention, whether considered to be related to the trial intervention or not.

Examples of Non-Serious Adverse Events (NSAE) related to participation in this study would

be:

Atrial fibrillation (irregular fast heartbeat causing palpitations);

Sternal pain;

Undue fatigue or exhaustion.

A Serious Adverse Event (SAE) would be regarded as an event which:

resulted in death;

is/was life threatening and/or required hospitalisation (unplanned or prolonged);

resulted in persistent or significant disability or incapacity;

resulted in surgical or medical intervention to prevent the above;

• is otherwise considered medically significant by clinical members of the study team.

Study participants will undergo clinical assessment after discharge following cardiac surgery

and be certified fit for CR by the clinical team. Before commencing exercise-based CR they

will undergo an ISWT, and CR will be tailored to their fitness levels. Exercise will be

supervised for centre-based programmes and remotely monitored for home-based

programmes. Participants undergoing home-based CR will be contacted by the CR team

throughout the rehab period to ensure correct safety measures are in place. At completion

of CR, they would have another assessment, including the ISWT, and an exit consultation.

These measures would reduce the risk and enable early detection of sternal complications

and enable early detection of possible complications. Any suspicion of the following

complications during CR or follow-up would warrant urgent medical consultation:

FARSTER-care Protocol

V2.0 22.10.2024

ISRCTN: 12204742

Sternal pain: Delayed sternal healing by forces or pressure not severe enough to disrupt

healing contributes to severe pain associated with tenderness along the sternotomy. This

may be confused with muscular or sternal wire pain, and paraesthesia which are more

common. This would be recorded as an AE which was related to study treatment but

expected.

Sternal instability: This is abnormal movement between the surgically divided sternum due

to delayed healing or non-union. This complication is rare. This would be considered an SAE.

Any study participant who complains of sternal wound pain or a feeling of "sternal click" will

be seen urgently by the surgical staff, examined, and investigated appropriately. All

NSAE/SAEs will be recorded. Participants who suffer adverse events with causality linked to

sternal instability will be given appropriate treatment, or surgery if required.

15.2 Collecting, recording and reporting of NSAE/SAEs

NSAE/SAEs will be collected, recorded and reported for participants from the point of

randomisation up to and including the twelve-month follow-up. Information about

NSAE/SAEs, whether volunteered by the patient, discovered by the clinical team questioning

or identified through physical examination, or recorded in the medical notes, will be

collected and recorded on the NSAE/SAE Report Form. The YTU should be informed of

NSAE/SAEs within the timeframes specified in the trial procedures.

When a participant has completed their twelve-month follow-up, it should be checked

whether there have been any unrecorded NSAE/SAEs for the participant before they exit the

trial. Any unresolved NSAE/SAEs should be followed up for one month after the participant

has exited the trial.

Adverse events that are deemed related to participation in this study and all SAEs will be

reported to the Chief Investigator (CI). Any SAEs deemed as 'related and unexpected' to

study intervention will be reported to the Sponsor, Research Ethics Committee (REC), DMC

and TSC.

FARSTER-care Protocol

V2.0_22.10.2024

Ongoing review of all AEs will take place during monthly Trial Management Group (TMG) meetings, discussed with the Patient Advisory Group (PAG), DMC and TSC and reported to the Sponsor and REC in line with their guidelines.

15.3 Safety monitoring plan

The RNs, CR staff and clinicians will record all NSAE/SAEs directly observed or reported by the trial participant from randomisation up to the final twelve month follow-up. In addition, sites should follow their own local procedures for the reporting of any adverse events linked to clinical care.

16. COMPLAINT HANDLING

The PIS will provide participants with contact details of the Sponsor in case of complaint. If there is negligent harm during the trial, when the NHS site owes a duty of care to the person harmed, NHS Indemnity covers NHS staff and medical academic staff with honorary contracts only when the trial has been approved by the Research and Development (R&D) department. NHS indemnity does not offer no-fault compensation and is unable to agree in advance to pay compensation for non-negligent harm.

17. DATA MANAGEMENT

17.1 Data collection

Table 2 outlines the data collection. Data collection will be carried out by appropriately trained members of the research team in each participating site using calibrated site equipment following standard site procedures. Data collection may take place at recruiting or CR sites. Recruiting sites will recruit participants and may also complete CR onsite, or alternatively, they may refer to CR sites.

For recruiting sites, all data collected will be entered onto a secure online Research

Electronic Data Capture (REDCap) interface, which will be designed and developed for this

study. Site staff will enter the data collected (Table 2) onto the REDCap database. Paper

FARSTER-care Protocol

V2.0_22.10.2024

IRAS reference: 334434 ISRCTN: 12204742

copies of the Case Report Forms (CRFs) can be used. If a paper copy is used by the clinical team at the site, then the clinical team at the site is responsible for inputting this data into REDCap. Participants will have the option to complete questionnaires electronically on REDCap or on paper. Where paper CRFs or questionnaires are completed, they are deemed to be the source data.

For CR sites, the data collected (Table 2) will be collected on paper CRFs and questionnaires. These will be posted to YTU, using pre-paid envelopes, where the data will be entered onto the REDCap database.

The trial team at YTU will manage the participant-reported data collection (participant questionnaires) at the twelve-month timepoint. To maximise the data collection at this timepoint, participants will have the option to complete the questionnaire electronically, by post or by telephone. Participants completing the questionnaire electronically or by post will be recontacted at two, four and five weeks after the initial contact was made. Of these, participants opting for email questionnaires will instead be contacted by post at four weeks. The contact attempt at five weeks will be by telephone for all these participants.

Participants who opt to complete the questionnaire by telephone will be contacted up to three times, which can be repeated 2 weeks later if necessary. If a participant cannot be contacted by telephone, a questionnaire may be posted to them. All questionnaires sent in the post will include a pre-paid envelope for the participant to return the questionnaire to YTU.

YTU will also manage the participant-reported data collection at the Pre- and Post-CR timepoints for participants who do not attend CR (if they are not deemed as fit for CR following the Outpatient Review or if they withdraw from CR by completing a Change of Status). As and when required, YTU may also send questionnaires to participants at other timepoints to support clinical teams.

To promote attendance at the six-month follow-up, during which visit the primary outcome measure is collected, participants will be sent a newsletter to optimise their engagement with the trial. Participants will also be offered £10 for completing their six-month follow-up, to cover for any travel costs. To enhance response rates of the twelve-month follow-up which consists of a participant questionnaire, participants will be sent a postcard thanking

them for their ongoing participation and support of their trial. YTU will coordinate the distribution of these documents.

Table 2. Data collection

Visit	Timepoint	Completed by	Site responsible	CRF capturing data
Eligibility	Prior to hospital discharge at week 0	Specialist clinical staff	Recruiting site	Eligibility Screening Checklist
Baseline	Prior to hospital	Specialist clinical staff/RN	Recruiting site	Clinician Baseline Form
baseiiile	discharge at week 0	Participant	Recruiting site	Participant Baseline Questionnaire
Outpatient review	6 weeks (control) or 3 weeks (intervention)	Specialist clinical staff	Recruiting site	Outpatient Review Form
	Queaks (control) or	Specialist CR staff	Recruiting or CR site	Clinician Pre-CR Form
Initial CR appointment	8 weeks (control) or 4 weeks (intervention)	Participant	Recruiting or CR site	Participant Pre-rehab Questionnaire (control/ intervention)
CR sessions	One or two times a week between 8 to 16 weeks (control) or 4 to 12 weeks (intervention)	Participant OR Specialist CR staff	Recruiting or CR site	Participant Exercise Session Form or Clinician Exercise Session Form
CR	16 weeks (sentral)	Specialist CR staff	Recruiting or CR site	Clinician Post-CR Form
programme completion	16 weeks (control) or 12 weeks (intervention)	Participant	Recruiting or CR site	Participant Post- rehab Questionnaire (control/ intervention)
6-month follow-up	26 weeks	Specialist clinical staff/specialist CR staff/RN Participant	Recruiting or CR site Recruiting or	Clinician 6-month (final) Form Participant 6-month
		·	CR site	Questionnaire
12-month follow-up	52 weeks	Participant	YTU	Participant 12-month Questionnaire

All information collected over the course of the study will be kept strictly confidential.

Participant's name, personal addresses, postcodes, NHS ID numbers and other contact details of consenting participants will be collected on the REDCap database, for the FARSTER-care Protocol

V2.0 22.10

purposes of assisting in follow-ups during the study. Participant data collected will all be pseudo-anonymised using a unique ID number and all related documents will use this ID number throughout the trial. Sites will be provided with a list of ID numbers and the research team at sites are responsible for allocating participants an ID number. Enrolment logs, which include patient-identifiable details, will be maintained at sites. A screening log will be used to capture information on the patients screened providing data on screening date, whether they were eligible or not (with reason) and if consented or not (with reason).

This log will not contain any patient-identifiable details.

17.2 Data storage

All work will be conducted following the University of York's data protection policy which is publicly available (University of York, 2017) [46]. Each site and YTU will hold data according to Good Clinical Practice guidelines, the Caldicott principles, the current Data Protection Act (2018) [47] and the General Data Protection Regulation (May 2018) [48].

Data, including patient-identifiable information, will be stored on the REDCap database, which is encrypted and password-protected. Access to the database will be restricted to delegated members of the site research team and the YTU trial team.

Electronic or scanned copies of documents used to collect trial data may be stored on the NHS or the University of York servers, which are accessed through password-protected computers. Patient-identifiable information may be stored on NHS servers (such as consent forms and enrolment logs), however no patient-identifiable information will be stored on university servers. Sensitive data that will be transferred between sites and/or computers will be transferred via encrypted methods, such as secure email.

Paper documents used to collect trial data will be stored at sites and YTU, and these will be retained in a secure location that is kept locked when not in use, for the duration of the trial. Paper CRFs and questionnaires may be returned to YTU from sites, by post using prepaid envelopes. There will be no patient-identifiable information included in these CRFs and questionnaires.

FARSTER-care Protocol IRAS reference: 334434

The University of York has a backup procedure as part of the University's Disaster Recovery process for central IT systems, allowing data to be restored in the event of a catastrophic failure. Backups are made on central file stores, and the backup service takes periodic copies of data on the file stores, meaning they can be restored to that point in time if needed.

17.3 Data quality assurance

Data collected as part of this research includes questionnaires, clinical assessments, and information from medical records. If data are found to be missing from participant completed questionnaires, or if data clarification or follow-up is required, participants will be contacted by either a RN or YTU research team member in an attempt to collect the data required. Therefore, participants will be asked for full contact details at baseline (including mobile phone number and email addresses) to enable this to occur.

Every attempt will be made to ensure the data are accurate, complete and reliable:

- The RNs and lead CR staff will be trained in collecting and reporting valid functional outcome measures (clinical assessments).
- Care will be taken to ensure participants are given clear instructions when completing the questionnaires and these will be checked for missing data by the clinic team before the participant leaves clinic.
- A source data form will be completed by each site to ensure suitable procedures are being followed to gather and store data.

18. SAMPLE SIZE AND STATISTICAL/ECONOMIC METHODS

18.1 Determination of sample size

In our external pilot trial, FARSTER, the mean and standard deviation (SD) of the ISWT pre-CR for the standard care group was 356.1m (174.2m) [39]. A study of CR participants found a minimum clinically important difference of 70m (95% CI 51.5–88.5) [49]. This study included a very comparable population of patients to FARSTER, with a similar mean pre-CR

ISWT of 390.8m (SD 173.1m). We shall conservatively power the trial to detect an Minimum Clinically Important Difference (MCID) of 52, which is the lower bound of the 95% CI for the MCID estimate. Assuming a SD of 174, this equates to a standardised effect size of 0.3. With 90% power, 5% two-sided significance, and 20% attrition (based on FARSTER), 588 patients will need to be recruited and randomised.

18.2 Statistical and analytical plans

For the analysis of the full trial (assuming continuation from the internal pilot trial), participant flow will be presented using a CONSORT diagram. Analyses will be conducted on an intention-to-treat basis unless otherwise stated. Baseline and outcome data will be summarised by group and overall. The ISWT distance will be analysed via mixed-effects repeated-measures linear regression, including site and participant as random effects. Randomised treatment group and clinically important participant-level covariates including gender, age and BMI will be included as fixed effects. CACE analysis using two-stage least-squares instrumental variable regression will be carried out to assess the treatment effect in participants whose actual timing of CR commencing complied with the timing which was allocated.

The secondary outcomes will be analysed using appropriate regression techniques based on the type of data controlling for the same covariates as included in the analysis of the primary outcome, plus baseline value of the outcomes where available.

Remote patient review and home-based CR are now common practice but the impact of these on clinical outcomes, PROMs and QoL are unknown. Details on intervention delivery and adherence will be presented, and baseline and outcome data will be summarised descriptively by group, stratified by whether patients received face-to-face or remote review, and home or centre-based CR.

Full analyses will be detailed in the trial's statistical analysis plan (SAP), which will be reviewed and approved by the trial steering and data monitoring committees and finalised prior to the end of data collection.

FARSTER-care Protocol IRAS reference: 334434

18.3 Health economics analysis

To inform objective four of the study to 'To conduct a detailed economic evaluation to assess the cost-effectiveness of early CR' we will conduct a number of analyses, consisting of the secondary outcome data collected in the trial (primarily EQ-5D-5L and resource use questionnaires alongside CR uptake) and the updating of an existing decision analytical model. These analyses will be considered in two parts: a within-trial analysis; and an extrapolated, model-based analysis.

The within-trial analysis will explore the costs and health outcomes associated with the interventions during the one-year trial follow-up period. This will take an NHS and PSS perspective, with costs estimated by applying published estimates of unit cost interactions to the frequency of NHS resource use reported through the participant questionnaires. Health outcomes will be estimated using the EQ-5D-5L generic health outcome questionnaire and used to inform estimates of quality adjusted life-years (QALYs) using the latest standardised UK value set. Additional economic metrics around out of pocket payments by the participants and the impact on employment will also be considered. Missing data will be described and imputed where appropriate using multiple imputation. In addition to summarising the total mean cost and QALYs for both arms during the within trial period, regression analysis will be used to explore the relationship between different variables. Stratification of results by clinically relevant characteristics including age, sex, and Index of Multiple Deprivation (IMD) status will also be explored. All within-trial analyses will apply methods consistent with the statistical analysis plan.

The extrapolated, model- based analysis will explore the potential longer-term cost-effectiveness of the two treatment approaches, an important consideration as the benefits of successful CR are expected to impact health outcomes and associated NHS resource use beyond the one-year trial follow-up. This model-based analysis will draw evidence from the FARSTER-care trial results, primarily the level of engagement with CR in the two arms, and the wider literature to interrogate whether the findings of the within-trial clinical and economic analyses are consistent with the longer-term cost-effectiveness implications, building on existing modelling analyses conducted by this team [50]. The existing model will be updated through a review of the latest effectiveness evidence, exploring whether the

FARSTER-care Protocol IRAS reference: 334434

V2.0_22.10.2024

Cochrane systematic review and meta-analysis that inform the original analysis remain up to

date. Extensive uncertainty analysis will be conducted including one way and probabilistic

sensitivity analysis to consider the sources and impact of uncertainty, commenting on the

potential value of future research to resolve it.

Both the within-trial and extrapolated analyses will additionally explore the implications of

the early and standard CR pathways stratified by socio-economic factors. For the within-trial

analysis this is expected to consist of stratification of the comparative analyses by patient

IMD, estimated for their residential area using lower-layer super output areas. The

extrapolated analysis will similarly stratify patients by IMD, consistent with the existing

decision model, additionally exploring the potential to conduct a distributional cost-

effectiveness analysis (DCEA) if relevant.

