• **Heart rate**: Measured in beats per minute using a pulse oximeter.

o **Blood pressure**: Systolic and diastolic blood pressure measured following

standard site procedure and recorded in mmHg.

Oxygen saturation: Measured using a pulse oximeter showing the percentage

of oxygen in the blood.

Patient outcomes

o Patient Reported Outcome Measure - Cardiac Rehabilitation (PROM-CR): A

patient-reported questionnaire designed and validated for cardiac

rehabilitation which asks a patient how much their heart condition has

impacted their life over the preceding two weeks in relation to physical, social

and lifestyle, emotional and care aspects [41].

Psychological health

o **Generalized Anxiety Disorder Scale (GAD-7**): The GAD-7 is a seven-item self-

administered patient questionnaire used as a screening tool and severity

measure for generalised anxiety disorder [42].

Quality of life

- EQ-5D-5L: The EQ-5D-5L is a validated generic patient-reported outcome measure [43, 44]. The descriptive system has five health domains (mobility, self-care, usual activities, pain/discomfort, and anxiety/depression) with five response options for each domain (no problems, slight problems, moderate problems, severe problems, and extreme problems). In addition, it has a health status Visual Analogue Scale (VAS) which measures self-rated health with endpoints ranging from 'the best health you can imagine' to 'the worst health you can imagine'.
- National Health Service (NHS) resource use
 - NHS resource use questionnaire: Patient reported NHS and Personal Social
 Services (PSS) resource use will be collected using bespoke questionnaire.

Complications

- These will be collected in the documentation at baseline and six months, and throughout the trial in the form of adverse events.
- CR uptake
 - o This will be recorded in the CR session logs.

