9. INITIAL CARDIAC REHABILITATION APPOINTMENT (PRE-CR TIMEPOINT)

Participants referred for CR will be offered a comprehensive programme including an assessment carried out at their initial cardiac rehabilitation appointment, prior to starting their programme in line with the recruiting sites' policies. The initial appointment will take place as near as possible to four weeks post-hospital discharge in the FARSTER-care group and as near as possible to eight weeks post-hospital discharge in the standard care group.

This appointment will be a face-to-face appointment where the participant will perform the ISWT and will be provided with advice on cardiac risk factor reduction. This will typically include information on medication, diet, exercise, and physical activity as well as psychosocial wellbeing and smoking cessation. Participants will be offered further education sessions on

cardiac risk factor reduction during the programme. These would be delivered by specialist CR staff. Referral to other healthcare professionals such as specialist counsellors, pharmacists and dieticians may also be considered if necessary. Unless contraindicated, referral to the exercise component of the CR programme will be made. Following this initial assessment, participants will be enrolled in exercise programmes. Data from the initial CR appointment will be recorded in the *Clinician Pre-CR Form*. If a participant does not attend this appointment, they will be sent another appointment.

During this appointment, participants will be asked to complete PROM-CR, EQ-5D-5L, GAD-7 and resource use questions (*Participant Pre-rehabilitation [control or intervention] Questionnaire*). If required, the trial team at YTU may send this questionnaire to the participant, either electronically or by post.

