11. CARDIAC REHABILITATION PROGRAMME COMPLETION (POST-CR

TIMEPOINT)

Following completion of the CR programme, at around 16 weeks post-hospital discharge for

control arm and twelve weeks post-hospital discharge for intervention arm, all study

participants will attend an appointment and have a repeat ISWT with data recorded in the

participant's Clinician Post-CR Form. A discharge letter will be sent to patients' General

Practitioner (GP) summarising their treatment. If a participant does not attend this

appointment, they will be sent another appointment.

During this appointment, participants will complete PROM-CR, EQ-5D-5L and GAD-7 questions

(Participant Post-rehabilitation [control or intervention] Questionnaire). If required, the trial

team at YTU may send this questionnaire to the participant, either electronically or by post.

FARSTER-care Protocol IRAS reference: 334434

V2.0_22.10.2024 ISRCTN: 12204742

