12. SIX MONTH FOLLOW-UP

About six months (26 weeks) after randomisation, all study participants will attend clinic to have an end-of-study consultation with a member of the research and/or the CR team. All study participants will undergo a final ISWT at this visit. Postoperative history including hospital attendance after discharge, clinical examination including sternal stability, and measurement of vital signs will be undertaken (see Figure 2: Study assessment schedule). Medical records will be checked for hospital readmissions and Accident & Emergency department attendance for surgery-related complications. Clinical data will be recorded on the *Clinician 6-month (Final) Form.* If a participant does not attend this appointment, they will be sent another appointment.

During this appointment, participants will complete PROM-CR, EQ-5D-5L, GAD-7 and resource use questions (*Participant 6-month Questionnaire*). If required, the trial team at YTU may send this questionnaire to the participant, either electronically or by post.

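### Resource use is self-reported at weeks 4 and 26 in one arm and weeks 8 and 26 in the other, so costs from weeks 0-8 carry recall error that differs by arm, in an unknown net direction

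*Protocol*

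**What the plan says.** Section 18.3 applies published unit costs to the "frequency of NHS resource use reported through the participant questionnaires", and the within-trial analysis covers costs and outcomes "during the one-year trial follow-up period". Section 3.2 says that "resource use will be collected using bespoke questionnaire" and gives no recall period.

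Resource use is asked three times:

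- **Pre-CR (section 9):** "participants will be asked to complete PROM-CR, EQ-5D-5L, GAD-7 and resource use questions". This appointment is to be as near as possible to "four weeks post-hospital discharge in the FARSTER-care group", and to eight weeks in the standard care group. Table 2 gives the same weeks.
- **Six months (section 12):** week 26 in both arms.
- **Twelve months (section 13):** week 52 in both arms.

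At post-CR (section 11; week 12 intervention, week 16 control) "participants will complete PROM-CR, EQ-5D-5L and GAD-7 questions", with no resource-use questions. Figure 2 agrees.

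Section 12 also states: "Medical records will be checked for hospital readmissions and Accident & Emergency department attendance for surgery-related complications". Section 18.3 does not name this check as a source of costs.

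**The concern.** The date of the first resource-use form is set by the allocated arm. The six-month form therefore looks back about 22 weeks in one arm and 18 in the other, and contacts in the first eight weeks are reported after different delays. If recall worsens with time, the arms are under-counted to different degrees even when true use is the same.

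The weeks most affected, 4-8, are those in which only the intervention arm is scheduled to be in CR, so they bear directly on the cost contrast in objective iv. A later analysis cannot recover contacts that were never reported: the multiple imputation in section 18.3 deals with missing answers, not forgotten contacts. This is a matter of the data-collection schedule, which the protocol itself fixes.

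**Working it through.** The protocol gives no recall figure of its own to reproduce, so the check starts from its schedule.

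**Inputs.** Resource-use forms at weeks 4, 26 and 52 (intervention) and 8, 26 and 52 (control), from sections 9, 12 and 13 and Table 2. Post-CR is at weeks 12 and 16 (section 11). Two assumptions are needed. First, each form covers the time since the previous one, which costing the whole year implies but the protocol does not state. Second, weeks from randomisation and weeks from discharge nearly coincide, since Table 2 places baseline before discharge at week 0.

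**Formula.** Recall for an event at week t = (week of the next resource-use form) - t.

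**Current schedule**

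| Event in weeks | Intervention | Control | Gap (intervention - control) |
|---|---|---|---|
| 0-4 | 4 - t: 0-4 | 8 - t: 4-8 | -4 |
| 4-8 | 26 - t: 18-22 | 8 - t: 0-4 | +18 |
| 8-26 | 26 - t: 0-18 | 26 - t: 0-18 | 0 |
| 26-52 | 52 - t | 52 - t | 0 |

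The gap is the same for every event within a row, so it does not depend on how events are spread inside the row.

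**Mean recall over weeks 0-26 if use is spread evenly**

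- Intervention: (4²/2 + 22²/2)/26 = (8 + 242)/26 = 250/26 = 9.6 weeks.
- Control: (8²/2 + 18²/2)/26 = (32 + 162)/26 = 194/26 = 7.5 weeks.
- Difference: 56/26 = 2.2 weeks.

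**Appointment window.** Section 7 allows 10 days either side (10/7 = 1.4 weeks). The longest recall at week 26 then runs from 20.6 to 23.4 weeks in the intervention arm and from 16.6 to 19.4 in control.

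**Direction.** As an illustration, suppose forgetting is linear in time and true use is equal in the arms. The two gaps cancel when use in weeks 0-4 is 18/4 = 4.5 times use in weeks 4-8. Below that ratio the intervention arm is under-counted more; above it, control is. The protocol gives neither the ratio nor a forgetting curve. Section 1.2 reports that complications are most frequent in the first week after discharge and lowest by four weeks, so complication-related use may well be concentrated in weeks 0-4.

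**With resource-use questions added at post-CR (4/12/26/52 and 8/16/26/52)**

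| Event in weeks | Intervention | Control | Gap |
|---|---|---|---|
| 0-4 | 0-4 | 4-8 | -4 |
| 4-8 | 4-8 | 0-4 | +4 |
| 8-12 | 0-4 | 4-8 | -4 |
| 12-16 | 10-14 | 0-4 | +10 |
| 16-26 | 0-10 | 0-10 | 0 |

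Mean recall becomes (8 + 32 + 98)/26 = 138/26 = 5.3 weeks (intervention) and (32 + 32 + 50)/26 = 114/26 = 4.4 weeks (control), a difference of 24/26 = 0.9 weeks. The longest recall before week 26 falls from 22 and 18 weeks to 14 and 10.

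**The case against.** The case for leaving the plan alone has several parts.

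- **The affected period is short.** Recall differs in 8 of the 52 weeks costed, and the large gap covers only 4. This stands.
- **Other sources exist.** CR attendance is taken from session logs and section 18.3 uses CR uptake alongside the questionnaires, so CR itself is not left to recall. Unplanned hospitalisation is an SAE whether or not related (section 15.1) and is collected to twelve months, including from medical notes (section 15.2). The six-month visit also takes a history of hospital attendance, and in the record-check sentence the surgery-related limit may apply only to A&E visits. All this stands, and it supplies part of the remedy. But section 18.3 names neither the SAE forms nor the record check as a cost source, and neither would capture routine GP, community or PSS contacts.
- **The form is not shown.** The recall period may be well worded. That does not remove the problem. A fixed look-back shorter than 18 weeks at week 26 would leave weeks 4-8 uncovered in the intervention arm only.
- **Adding a post-CR form creates new differences.** This is correct: recall is now equal in weeks 8-16, and would then differ by 4 weeks (weeks 8-12) and 10 weeks (weeks 12-16).

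A reader might also infer three stronger things that the documents do not support. One is that the design favours early CR: the reversed gap in weeks 0-4, where complications peak, prevents that conclusion. Another is that recall is up to 22 weeks in one arm and never more than 8 in the other: those maxima belong to different events, and controls also recall up to 18 weeks for events after week 8. The third is a count of lost contacts: the protocol gives no contact rate and no forgetting rate.

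**Conclusion.** The concern holds as a design weakness confined to weeks 0-8. Recall is 18 weeks longer in the intervention arm for use in weeks 4-8, 4 weeks longer in control for use in weeks 0-4, and equal from week 8. This is differential measurement error in the within-trial cost comparison. Its net direction and its size in money cannot be derived from the protocol.

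The result rests on each form covering the time since the last one, and on appointments falling near their stated weeks. The primary outcome is unaffected. The change is worth making because it is cheap and works only prospectively.

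**What to change.** 1. **Hospital use.** In section 18.3, take inpatient stays and A&E attendances for weeks 0-26 in both arms from the six-month medical-record check. Reword that check in section 12 as all-cause, with dates. Supplement it with the SAE hospitalisation reports already collected to twelve months, and keep self-report as a sensitivity analysis. The window and method are then the same in both arms.
2. **GP, community and PSS use.** Add the resource-use questions to the existing post-CR questionnaire (section 11 and Figure 2). The weeks 4-8 gap falls from 18 to 4 weeks, the longest recall from 22/18 to 14/10 weeks, and the mean difference over weeks 0-26 from about 2.2 to 0.9 weeks.

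**Cost.** A few more minutes per form and per record check, a wider dated field on the six-month clinician form, and a sentence in section 18.3. No visit is added. Two limits should be stated openly: a 10-week recall gap for events in weeks 12-16 (with a 4-week gap in weeks 8-12), and admissions to other hospitals that may still rest on self-report.
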